Medical adherence is a critical aspect of patient management and ultimately clinical outcomes. Therefore, we will assess both general medical adherence and medication adherence: 1) Medical Adherence. Adherence to medical regimen will be assessed using the Health Habits Survey (HHS). The HHS is a self-report measure of behavioral compliance that uses an ordinal response format to determine post-transplant adherence in 10 areas: (i) taking medications in general; (ii) taking the primary immunosuppressant (IS; cyclosporine or tacrolimus); (iii) attending clinic appointments; (iv) completing blood work; (v) monitoring home blood pressure, (vi) following a prescribed diet; (vii) following the prescribed exercise plan; (vii) abstaining from tobacco use; (ix) limiting alcohol consumption; and (x) performing home spirometry. Responses for each element will be adjudicated based on the minimum level acceptable according to programmatic guidelines set forth by our study pulmonologists. To estimate overall adherence, elements are summed for a total score (range 0-10). 2) Medication Adherence. Because medication adherence is critical to the success of solid organ transplantation, we will rely on biologic markers of medication adherence. In addition to our self-report assessment of medication adherence, we will validate participants' self-reported adherence levels using blood assays, which are routinely obtained in our transplant clinics. Blood assay markers for tacrolimus (FK) and cyclosporine (CsA) are performed at each clinic visit using a therapeutic range for each drug based on clinical guidelines (e.g., CsA: 100-150 ng/mL and FK: 5-10 ng/mL for most patients). Trough blood level results will be combined using the non-therapeutic blood assay variability of FK and CsA, in which the percentage of sub- or supra-therapeutic FK / CsA assays are calculated by dividing the number of assays outside individually determined, recommended levels divided by the total number of FK / CsA assessments taken. Blood levels assessed >3-months following transplant will be used for baseline assessments, in order to allow for individual variability in initial metabolic adaptation to postoperative medication changes.

No blood will be drawn as part of the study.

Global psychological distress will be measured using a battery of questionnaires composed of composed of BDI-II, GHQ, STAI, PSS, and PROMIS Anger;

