The primary endpoint will be a global measure of distress. Secondary outcomes will include measures of functional capacity, coping, self-efficacy, PA, health behaviors, frailty, and medical outcomes (i.e., CLAD), the latter of which will be documented by annual follow-up visits of up to 4 years (median >2 years).

All analyses will follow the intention-to-treat (ITT) principle, including all patients who were randomized. Patterns of missing data will be characterized using Rubin's criteria and managed accordingly using Harrell's multiple imputation (mult.impute) procedure in R. We will supplement the ITT analysis with an examination of the treatment effect among completers using Rubin's Complier Average Causal Effect (CACE) model.

We will test our primary hypotheses using the "gatekeeper" approach, which has been shown to maintain the experiment-wise error rate while maximizing power when testing multiple endpoints. This type of methodology has been widely advocated in RCTs involving medical populations as a parsimonious strategy to control type-I error within the first (i.e. "gatekeeper") step, because a favorable result on any individual component observed by chance is unlikely to be overly influential to the composite as a whole. Because the type-I error is minimized at this stage of analysis, the familywise error rate can then be propagated to the second analysis stage, examining individual components. In contrast, error correction to individual components of the composite often over-controls for type-I error when the purpose is explanatory. In order to mitigate Type-I error with multiple outcomes, we will partition the conventional alpha = .05 to test treatment effects on Global distress and Functional capacity each at alpha = .025. Thus, for our examination of global distress changes, an experiment-wise p-value of .025 will be used to assess significance. If this test fails to be rejected at p-value < .025, then tests of individual components are not interpreted. However, if improvements in global distress are found, examination of changes in individual components of distress are carried out in a secondary, explanatory step. Consistent with contemporary recommendations, secondary outcomes will be considered as potentially supportive and therefore examined at the alpha = .05 for each domain.

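### The plan says familywise error control carries through the gatekeeper to the five distress scales, but one gate followed by unadjusted tests gives only weak control

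*Combined protocol and SAP*

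**What the plan says.** All statements except the list of scales are in Data Analysis & Statistical Considerations.

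- **Alpha split.** The plan will "partition the conventional alpha = .05 to test treatment effects on Global distress and Functional capacity each at alpha = .025". For global distress, "an experiment-wise p-value of .025 will be used to assess significance".
- **Gate.** "If this test fails to be rejected at p-value < .025, then tests of individual components are not interpreted". If the global test succeeds, "examination of changes in individual components of distress are carried out in a secondary, explanatory step".
- **Components.** The battery, listed under Demographic, Medical history information, and Adherence, is "composed of BDI-II, GHQ, STAI, PSS, and PROMIS Anger", so five scales stand behind the gate.
- **Claims for the procedure.** The gatekeeper approach "has been shown to maintain the experiment-wise error rate while maximizing power when testing multiple endpoints", and after the first step "the familywise error rate can then be propagated to the second analysis stage, examining individual components".
- **Adjustment among components.** None is specified. The plan argues against it: "error correction to individual components of the composite often over-controls for type-I error when the purpose is explanatory".
- **Component alpha.** Not stated. The section gives .05 per domain for secondary outcomes, but its list of secondary outcomes does not include the distress scales.

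**The concern.** The gate protects the component tests when CSTEX affects none of the five scales, because a false component claim then needs a false global result first. That protection goes once some scales truly improve. The real effects open the gate, and each unaffected scale then has its own chance of a false positive. The components are interpreted only after a positive global result, so this mixed case is the one that matters in practice.

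At stake is what can be said about which aspect of distress improved: depression, general distress, stress, anxiety or anger. As the text stands, a report could cite the plan as showing that statements about single scales are error-controlled at the familywise level. The procedure described does not deliver that.

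**Working it through.** **Inputs from the documents.** Gate alpha .025; five scales; equal allocation; up to 180 participants with 15% attrition, so 180 × 0.85 / 2 = 76.5, taken as 76 per arm; covariate–outcome correlation 0.53, so residual SD = √(1 − 0.53²) = √0.7191 = 0.848; d = 0.44 from the power statement.

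**Assumptions the documents do not settle.** Two-sided tests; composite equal to the mean of the standardised scales; equal pairwise correlations r of 0.3 to 0.7; one to three scales truly affected and the rest exactly null; effects up to d = 0.8; component alpha .025 (carried over from the gate) or .05 (if the scales are treated as secondary outcomes).

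**1. The plan's own figure.** .025 + .025 = .05. The split between global distress and functional capacity is correct.

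**2. All five scales null.** A false component claim requires a false gate, so its probability is at most .025. Simulation gives .013 to .025. This is weak control, and the plan has it.

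**3. Some scales affected.** With m null scales tested at level a, independent scales and a gate certain to open, P(any false claim) = 1 − (1 − a)^m:

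- m = 2, a = .025: 1 − .975² = .049
- m = 3, a = .025: 1 − .975³ = .073
- m = 4, a = .025: 1 − .975⁴ = .096
- m = 2, a = .05: 1 − .95² = .0975
- m = 4, a = .05: 1 − .95⁴ = .185

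These are limiting values. Correlation among the scales lowers them, and so does a gate that may stay shut.

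**4. Allowing for correlation and the gate.** Simulation with 76 per arm, r = 0.3–0.7, and one to three scales affected at d = 0.44 or 0.8:

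| Component rule after the gate | Any false component claim | Multiple of .025 |
|---|---|---|
| Unadjusted at .025 | 2.1–4.8% | 0.8–1.9 |
| Unadjusted at .05 | 4.2–9.5% | 1.7–3.8 |
| Holm, total .025 | 1.0–2.4% | 0.4–1.0 |

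The top of each unadjusted range can be checked by hand. With three scales affected at d = 0.8 and r = 0.3, each affected scale's test statistic is shifted by (0.8 / 0.848) × √(76/2) = 5.8. The composite is shifted by (3/5) × 5.8 / √((1 + 4 × 0.3)/5) = 5.3, against a critical value of 2.24, so the gate is almost certain to open. Two null scales remain, and the independent limits of .049 and .0975 fall slightly with correlation, to about .048 and .095.

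At the plan's own d = 0.44 with components at .025, the rate is about 2–3.4%, at most about 1.4 times .025. Some settings stay below .025; the lowest is three scales affected at d = 0.44 with r = 0.7. At .05, every mixed setting examined exceeds .025.

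**The case against.** The strongest reply is that the plan does not present the component tests as confirmatory. It places type-I control in the gatekeeper step, calls the component step secondary and explanatory, and openly declines correction for that reason. That is a legitimate and disclosed choice. This part of the reply stands, so Holm should not be presented as obligatory. But the same paragraph also says that the error rate is maintained across multiple endpoints and propagated to the components. The plan cannot decline correction because the step is explanatory and also claim familywise control for it.

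A second reply is that the scales overlap. By the protocol's own description, the GHQ covers anxiety and depression among other things, so a large effect on the BDI-II with none at all on the GHQ is not very plausible. High correlation and few truly null scales both reduce the error. This also stands, and it is why the realistic size is modest.

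A reader might infer that false component claims occur at about four times .025. The documents do not support that as the size. With components at .025, a value near .10 needs four null scales, near-independence and a gate almost certain to open; with uncorrelated scales, that means an effect near d = 1.8 on a single scale. Even with the gate certain to open, the four-null figure falls to .082 at r = .5 and .069 at r = .7. The simulated 9.5% needs components tested at .05, which the plan does not assign to them, together with d = 0.8 on two or three scales and r = 0.3. Under that reading, a single null scale behind an open gate already gives .05, twice .025 with no multiplicity at all, so part of the excess is a mismatch of alpha levels.

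**Conclusion.** The point holds as an overstated claim. The procedure gives weak familywise control over the five scales, not the control that the text asserts. In mixed scenarios, the chance of at least one false component claim is about 2–5% with components at .025 (roughly 1–2 times .025) and about 4–9.5% at .05. Which range applies is unknown, because the component alpha is not stated. Both ranges rest on the assumed correlations, the equal weighting, and the assumed number and size of true effects. Only d = 0.44 comes from the documents.

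A reader might go further and infer that the trial makes unprotected confirmatory claims on single scales. The plan's labelling of the step as secondary and explanatory does not support that. The global distress test, its alpha and the sample size are unaffected.

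**What to change.** Delete the statements that error control is maintained for, or propagated to, the individual components. State that, after a significant global test, component estimates will be reported with confidence intervals as descriptive, without significance claims. This costs a few sentences of SAP wording and the claim itself. It agrees with the plan's own description of the step and removes the need to choose a component alpha.

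If the sponsor wants to keep the familywise claim, test the five components with Holm at a total alpha of .025 after the global test passes. The smallest p-value is compared with .025/5 = .005, the next with .025/4 = .00625, and so on. In the simulations this kept the rate at or below 2.4%. The cost is somewhat lower power for single scales.

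Under either option the primary test stays as planned.

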Improving Lung Transplant Outcomes with Coping Skills and Physical Activity

INSPIRE III

Document Date: May 2, 2024

NCT04093869

Purpose of the Study

The study will aim to evaluate the effectiveness of the Coping Skills Training plus Exercise (CSTEX) intervention in reducing distress. It is hypothesized that compared to Standard of Care plus Education (SOC-ED), the CSTEX intervention will result in greater reductions in global distress measured by an established psychometric test battery. Additional secondary outcomes will include measures of functional capacity assessed by distance walked on a standard Six Minute Walk test (6MWT), physical activity (PA) during daily life, QoL, sleep quality, coping and self-efficacy, measures of frailty, and clinical outcomes defined as CLAD-free survival, a well-established clinical outcome following lung transplantation. We also will explore possible mechanisms by which the CSTEX intervention may reduce distress, increase functional capacity, and improve medical outcomes, including enhanced coping skills, increased self-efficacy, greater PA, and better adherence to prescribed medical therapies (including immunosuppressant medications, regular exercise, and monitoring of pulmonary function). We will test the hypothesis that CSTEX, a post-transplant intervention combining CST and exercise, will reduce distress. We also hypothesize that CSTEX will promote such health behaviors as increased functional capacity, daily PA and medication adherence, enhance psychological QoL, and potentially improve clinical outcomes

Background & Significance

For patients with end-stage lung disease, lung transplantation is now a viable treatment option to improve their quality of life (QoL) and extend their survival. With the growing number of individuals with advanced lung disease, most commonly idiopathic pulmonary fibrosis (IPF), chronic obstructive pulmonary disease (COPD), and cystic fibrosis (CF), the frequency of transplant has increased exponentially over the past 20 years, with nearly 42,000 patients having been transplanted; more than 2,500 individuals were transplanted in 2016, which is projected to continue to increase in the future. Public health expenditures due to chronic lung diseases are estimated to reach \$832 billion in 2021.

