With respect to changes in global distress, we estimated power using a correlation of 0.53 between covariates and the outcome, an initial sample size of 150 participants (amended to up to 180 participants), attrition of 15%, and an alpha of 0.025. Based on these assumptions, we will have 80% power to detect a small-to-moderate treatment size difference (d = 0.44), comparable to what we observed in our prior work among pre-transplant candidates. For changes in functional capacity and PA, we should have 80% power to detect even small differences in 6MWD (d = 0.21) and total daily actigraphy steps (d = 0.32). As an exploratory aim, we also will examine the impact of CSTEX on clinical outcomes. Power for our exploratory clinical event models was estimated assuming a conservative event rate of 75% in the control group, 42 months for patient accrual, a median follow-up of 30 months and a minimum follow-up time of 6 months. At an alpha of 0.05, and 75 patients per group, we will have

80% power to detect a 64% event rate reduction. We will carefully examine all model assumptions and reparameterize as indicated. All analyses will be carried out using SAS (Cary, NC) or R (http://cran.r-project.org/) software.

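### Functional capacity (6MWD) is assigned alpha 0.025 in the split but also falls under the 0.05-per-domain rule for secondary outcomes, and nothing says which governs

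*Combined protocol and SAP*

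**What the plan says.** Three statements in Data Analysis & Statistical Considerations bear on this.

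- **Status.** Global distress is named as the primary endpoint, and then: "Secondary outcomes will include measures of functional capacity, coping, self-efficacy, PA, health behaviors, frailty". The Purpose of the Study agrees: "Additional secondary outcomes will include measures of functional capacity assessed by distance walked".
- **Split.** "we will partition the conventional alpha = .05 to test treatment effects on Global distress and Functional capacity each at alpha = .025". The next sentence draws the consequence for distress only: "for our examination of global distress changes, an experiment-wise p-value of .025 will be used to assess significance".
- **Secondary rule.** The paragraph closes with "secondary outcomes will be considered as potentially supportive and therefore examined at the alpha = .05 for each domain". No outcome is excepted.

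The power paragraph that follows gives an alpha for global distress ("attrition of 15%, and an alpha of 0.025") and for the exploratory clinical events ("At an alpha of 0.05, and 75 patients per group"). Between the two, it claims 80% power for a 6MWD difference of d = 0.21 without stating an alpha.

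**The concern.** Read together, these sentences give 6MWD two significance thresholds: 0.025 by name, and 0.05 as a member of the secondary class. An analyst could cite the plan for either one.

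Functional capacity is the only outcome besides distress that receives a share of alpha, and half of the intervention is exercise, so a 6MWD result is likely to be reported prominently. If its p-value lands between 0.025 and 0.05, success or failure would depend on which sentence is invoked after the result is known. The split keeps error for distress and 6MWD at 5% or less only if 6MWD is judged at 0.025.

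**Working it through.** **Inputs.** From the analysis section: total alpha 0.05, split 0.025 + 0.025; secondary rule 0.05 per domain; 80% power for 6MWD at d = 0.21; N = 150 (amended to up to 180); attrition 15%. Assumed, because the plan is silent: two-sided tests, and correlations of 0, 0.3 and 0.5 between the two test statistics. A normal approximation is used, with z(0.9875) = 2.2414, z(0.975) = 1.9600 and z(0.80) = 0.8416.

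**1. The plan's own split.** 0.025 + 0.025 = 0.05, as stated. With 6MWD at 0.05 instead, the sum is 0.025 + 0.05 = 0.075.

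**2. Error for the pair.** This is 1 − P(|Z1| < z1, |Z2| < z2), with both nulls true and bivariate normal statistics. For independent tests:
- both at 0.025: 1 − 0.975 × 0.975 = 0.0494
- 0.025 and 0.05: 1 − 0.975 × 0.95 = 0.0737

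| Correlation | Both at 0.025 | Distress 0.025, 6MWD 0.05 |
|---|---|---|
| 0 | 4.9% | 7.4% |
| 0.3 | 4.8% | 7.2% |
| 0.5 | 4.6% | 6.9% |

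**3. Chance that the 6MWD p-value falls between the two thresholds.** Under the null: 0.05 − 0.025 = 2.5%. Under the alternative, anchoring on the stated 80% power means that no 6MWD correlation or attrition has to be assumed:
- 80% set at 0.025: noncentrality 2.2414 + 0.8416 = 3.083. Power at 0.05 is Φ(3.083 − 1.960) = 0.869. Difference: 6.9%.
- 80% set at 0.05: noncentrality 1.9600 + 0.8416 = 2.802. Power at 0.025 is Φ(2.802 − 2.241) = 0.712. Difference: 8.8%.

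A noncentral t calculation with 150 × 0.85 / 2 = 63.75 or 180 × 0.85 / 2 = 76.5 per arm gives nearly the same: 7.1% and 9.0%, with power 0.710 in place of 0.712.

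**4. Consequence for the power statement.** If the 80% was computed at 0.05, power at 0.025 is about 71%. Keeping 80% would need d = 0.21 × 3.083 / 2.802 = 0.231.

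**5. Does d = 0.21 reveal which alpha was used?** Solve for the covariate correlation that it implies: r = √(1 − [d / (√(2/n) × (z(1−α/2) + z(0.80)))]²). With n = 63.75:
- alpha 0.025: 0.21 / (0.1771 × 3.083) = 0.385, so r = 0.92
- alpha 0.05: 0.21 / (0.1771 × 2.802) = 0.423, so r = 0.91

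No 6MWD correlation is given, so the figure cannot tell the two apart.

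**The case against.** The strongest reply is that a specific rule governs a general one. The 0.025 sentence names functional capacity and attaches a number; the 0.05 sentence names no outcome; and the partition would serve no purpose if 6MWD were tested at 0.05. The plan also speaks of primary hypotheses in the plural, and the Background gives improving functional capacity as an aim of the trial alongside reducing distress. This makes 0.025 the likelier intent. It does not make it the stated rule: the same section names a single primary endpoint and puts functional capacity first in the list of secondary outcomes.

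Three further points limit the weight of the concern, and they stand.

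- The 7% error needs a mixture that neither rule authorises: the 0.05 threshold from the supportive class combined with a confirmatory claim. It describes what the ambiguity permits, not what either sentence prescribes.
- The absence of a follow-on sentence for functional capacity is weak evidence. The distress sentence leads into the gate for the components of a composite, and 6MWD has no components.
- The 71% is conditional on the 80% being sound and having been computed at 0.05. With the only correlation the plan states (0.53, given for distress) and 63.75 per arm, the noncentrality is 0.21 / (√(1 − 0.53²) × 0.1771) = 1.40. Power is then about 20% at 0.025 and 29% at 0.05. The unstated 6MWD correlation matters more to power than the choice of alpha.

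None of this removes the freedom to choose a threshold when p lies between 0.025 and 0.05.

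**Conclusion.** The concern holds. This is a conflict between two written decision rules for one outcome, and it should be fixed. The firm part is textual: 6MWD is at 0.025 under the split, at 0.05 as a listed secondary outcome, with no exemption and no alpha on its power statement.

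The direct consequence is a result open to either call, with the probabilities in step 3. The excess in pair error, to about 7% from under 5%, arises only if 6MWD is claimed as confirmatory at 0.05. The fall in power to about 71% arises only if the stated 80% was computed at 0.05. The figures rest on two-sided tests and a normal approximation. The distress threshold and the primary conclusion are not affected.

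**What to change.** Before results are seen:

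1. In the closing sentence of the multiplicity paragraph, after the words secondary outcomes, insert: *other than functional capacity (6MWD), which is tested at 0.025 under the alpha split,*. The 0.05-per-domain rule then applies to the remaining secondary outcomes. Global distress stays the only primary endpoint, and 6MWD becomes an alpha-controlled secondary outcome outside the supportive group. The plan should say this in so many words, so that the standing of a 6MWD result below 0.025 is clear.
2. In the power paragraph, state alpha 0.025 for the 6MWD figure. If it was computed at another alpha, update the power or the detectable d.

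The cost is one clause and one stated alpha. The endpoint hierarchy, the distress threshold and the split do not change. The downside is a stricter threshold for 6MWD than the 0.05 reading would give, and a lower stated power if the 80% was set at 0.05.

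### Is the stated 80% power for six-minute walk distance at d = 0.21 wrong, given that no printed input produces it?

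*Combined protocol and SAP*

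**What the plan says.** All the relevant text is in the combined protocol and SAP, under Data Analysis & Statistical Considerations.

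- The power paragraph opens with the primary endpoint: "With respect to changes in global distress, we estimated power using a correlation of 0.53 between covariates and the outcome". It adds 150 participants (amended to up to 180), 15% attrition and alpha 0.025, and arrives at 80% power for d = 0.44.
- The next sentence turns to other outcomes: "we should have 80% power to detect even small differences in 6MWD (d = 0.21) and total daily actigraphy steps (d = 0.32"). For these it prints no correlation, alpha or SD scale.
- On alpha, the plan will "test treatment effects on Global distress and Functional capacity each at alpha = .025".
- The same section also says "Secondary outcomes will include measures of functional capacity, coping, self-efficacy, PA, health behaviors, frailty", and that "secondary outcomes will be considered as potentially supportive and therefore examined at the alpha = .05 for each domain".

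**The concern.** A reader who carries the distress inputs over to 6MWD finds power far below 80%. With r = 0.53, alpha .025 two-sided and 15% attrition, power at d = 0.21 is 20% for N = 150 and 24% for N = 180. The stated 80% would then look like an arithmetic error.

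The point has some weight because functional capacity receives half of the conventional alpha, and d = 0.21 is the plan's only statement of how sensitive that test is. If the figure were too optimistic, a null 6MWD result might be read as excluding a small effect that the trial could not in fact detect. The two statements on alpha, .025 for functional capacity and .05 for secondary outcomes, add to the impression that the figure cannot be checked.

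**Working it through.** **Inputs.** From the plan: equal allocation, N = 150 or 180, attrition 15% (127.5 or 153 evaluable), alpha .025 or .05, power 80%, r = 0.53 for distress. Assumed: two-sided test, covariate-adjusted comparison of means, d in units of the unadjusted SD.

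**Formula.** Detectable d = (z for alpha + z for power) × sqrt(1 − r²) × sqrt(4/N). The z-sum is 2.241 + 0.842 = 3.083 at alpha .025 and 1.960 + 0.842 = 2.802 at alpha .05.

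**The plan's distress figure.** With r = 0.53, sqrt(1 − 0.2809) = 0.848.

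- N = 127.5: 3.083 × 0.848 × 0.1771 = 0.46
- N = 153: 3.083 × 0.848 × 0.1617 = 0.42

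The printed 0.44 lies between these. Power at d = 0.44 is 75% and 83%. The formula therefore brackets the plan's figure without hitting it exactly.

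This also supports the assumed scale. If d were in units of the residual SD, the factor 0.848 would drop out and the detectable effect would be 0.55 / 0.50, further from 0.44.

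**Correlation needed for 6MWD at d = 0.21.** Solve r = sqrt(1 − (d/m)²), where m = z-sum × sqrt(4/N).

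| Alpha (two-sided) | N evaluable | m | Required r |
|---|---|---|---|
| .025 | 127.5 | 0.546 | 0.92 |
| .025 | 153 | 0.499 | 0.91 |
| .05 | 127.5 | 0.496 | 0.91 |
| .05 | 153 | 0.453 | 0.89 |

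The most lenient design (N = 180, no attrition, one-sided .05) still needs r = 0.82.

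**Calibration to the plan's own result.** Taking 0.44 at r = 0.53 as given, k = 0.44 / 0.848 = 0.519. At the same alpha, sample size and sidedness:

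- 6MWD: r = sqrt(1 − (0.21/0.519)²) = 0.91
- Steps: r = sqrt(1 − (0.32/0.519)²) = 0.79

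Here k corresponds to 4 × (3.083/0.519)² ≈ 141 evaluable patients, which is none of 127.5, 150, 153 or 180. The calibration is therefore a consistency check and does not recover the authors' exact inputs.

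**Steps at alpha .05.** With 127.5 or 153 evaluable patients, d = 0.32 needs r = 0.76 or 0.71.

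**Reading.** The same sample with the same power cannot yield 0.44, 0.21 and 0.32 from one correlation and one alpha. Moving from alpha .025 to .05 only multiplies the detectable effect by 2.802/3.083 = 0.91. The three values make sense only if something else differs by outcome, and the correlation is the natural candidate.

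**The case for a change.** The best case for a change is that r of about 0.9 is a demanding value: covariates would explain about 84% of the variance in 6MWD (0.914² = 0.836), against 28% for distress (0.53² = 0.281). If the true value is lower, power falls quickly. At alpha .025 with 15% attrition it is 68% / 77% at r = 0.90, 40% / 47% at r = 0.80 and 28% / 34% at r = 0.70 (N = 150 / 180). If d were on the residual-SD scale, no correlation would rescue the figure, and 712 (alpha .05) to 864 (alpha .025) evaluable patients would be needed. Printing the correlation and its source would cost little.

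What stands is that the input is missing and a reader cannot verify the figure. What does not follow is that the figure is wrong. The documents give no correlation for 6MWD, so none of these rows can be called this trial's power. The rows using 0.53 are the least apt, since the plan reserves that value for distress. The residual-SD reading fits the plan's own distress figure less well.

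The alpha question does not rescue the case. The .025 is assigned to functional capacity by name, while the .05 is a general rule for secondary outcomes, so the specific statement can be taken to govern. The choice moves the required correlation only from 0.92 / 0.91 to 0.91 / 0.89.

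**Conclusion.** The concern is right that d = 0.21 for 6MWD cannot be reproduced from the printed inputs. Under a two-sided covariate-adjusted test, with d on the unadjusted SD scale and 15% attrition, the figure implies a correlation of about 0.9 (0.89 to 0.92 across the two sample sizes and two alphas). The steps figure implies a more moderate one, 0.71 to 0.76 at alpha .05.

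This is an unreported input and not a demonstrated error. The distress correlation was not offered for 6MWD, and the spread of detectable effects suggests outcome-specific values. The printed sample size calculation concerns distress, so documenting the 6MWD correlation would alter neither the number of patients nor the analysis. Whether the figure would need restating depends on a value that the documents do not contain. When the trial reports, the precision of the 6MWD comparison can be judged from its own confidence interval, whatever correlation was assumed in planning. No change to the plan is called for.
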